Pediatrics, a multi-center neonatal genetic screening research project was launched in China with 8 provincial and municipal tertiary hospitals. 159 genes of 156 common genetic diseases were selected for sequencing screening. At present, nearly 30,000 samples have been analyzed, the positive detection rate is close to 4.0 %, and the carrying rate is 51.98 %. The results show that neonatal genetic screening combined with existing biochemical screening shows obvious advantages, which can detect disease risk earlier, reduce missed diagnosis of conventional new screening, provide detection rate, assist rapid diagnosis of diseases, early intervention, and reduce family and social harm.

In Guangdong Province, our research team took the lead in carrying out a preliminary study of neonatal genetic screening. From June 2019 to April 2020, our team also completed a study of neonatal genetic screening in 1739 cases of Guangzhou Science and Technology Plan Project in Guangdong Province. In this study, high-throughput sequencing technology based on target gene capture was used to detect common genetic disease genes in heel blood samples. The results showed that a total of 158 positive cases were screened out, with a positive rate of 8.81 %. A total of 972 cases carried one or more gene pathogenic variation sites, with a carrying rate of 54.21 %, suggesting that the pathogenic variation of common neonatal genetic diseases has a high incidence and carrying rate in Guangdong, but the study has the problem of insufficient sample size. Compared with the results of traditional neonatal mass spectrometry screening, we found that gene screening has obvious advantages, which effectively reduces the false positive rate and false negative rate of screening, significantly expands the diseases of neonatal genetic disease screening, makes disease diagnosis and typing faster and more accurate, and can specifically design the diseases and genes of gene screening according to regional or ethnic differences.

In recent years, the application of ' artificial intelligence +' in the medical field has become a hot spot of modern science and technology. The medical industry is highly complex and professional. Artificial intelligence can play a role in many aspects, including medical image recognition, auxiliary diagnosis, drug research and development and other fields. Recently, an artificial intelligence-assisted diagnostic

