3.1 Research Design

This study is a multi-center cooperative study of the South China Neonatal Genetic Screening Alliance. The principal investigator (PI) and project leader of this study are [name], chief physician of pediatrics of the Sixth Affiliated Hospital of Sun Yat-sen University, who plans to include 123 cooperative units of the South China Neonatal Genetic Screening Alliance. In this study, 40,000 neonatal genetic screening data and MS / MS data were retrospectively analyzed through multi-center cooperation. The collection date was from January 2019 to August 2022.

Through the statistical analysis of neonatal genetic screening data (138 genes related to 133 common genetic diseases), the incidence of common genetic diseases in newborns in China, the carrying rate of pathogenic variation and the high-frequency variation sites of the population were clarified, and the epidemiological characteristics of newborns in China were studied.

Through the statistical analysis of neonatal genetic screening data and MS / MS metabolomics data (11 amino acids and 28 acylcarnitines), the correlation between gene and metabolism will be explored, and the pathogenicity of high-frequency VUS mutation sites will be identified by using protein function artificial intelligence analysis platform and tandem mass spectrometry metabolite data.

The prediction model of common genetic diseases is constructed by using machine learning algorithms such as random forest, support vector machine, elastic network and multi-layer perceptron, so as to realize the accurate diagnosis of common genetic diseases through tandem mass spectrometry metabolomics data, and expand 2-3 kinds of diseases that can be detected by MS / MS technology.

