3.1 Sample size

This study plans to collect genetic screening data (138 genes related to 133 common genetic diseases) and tandem mass spectrometry metabolomics data (11

amino acids and 28 acylcarnitines) of about 40,000 newborns from January 2019 to August 2022 in 123 cooperative units of the South China Neonatal Genetic Screening Alliance.

3.3 data collection

In the course of the study, no random or any treatment driven by the research program will be performed or provided to the subjects. The researchers will view the patient 's medical history and laboratory reports, and determine the patient 's eligibility according to the inclusion and exclusion criteria.

(1) The types of diseases detected by genetic screening : including 133 kinds of hereditary diseases with high incidence in neonates. The types of diseases include genetic metabolic diseases such as amino acid metabolic diseases, organic acid metabolic diseases and fatty acid metabolic diseases within the scope of all neonatal tandem mass spectrometry screening, as well as other genetic diseases that cannot be screened by tandem mass spectrometry but have high incidence and early detection of great clinical significance and social benefits for children and families, such as lysosomal diseases, glycogen accumulation diseases, hepatolenticular degeneration, hereditary deafness, β -thalassemia, etc.

(2) In this study, the data analysis of genes and the interpretation of test reports are based on the implementation of industry consensus or guidelines for genetic testing of genetic diseases such as ' Discussion on the standardized consensus of the whole process of clinical detection of genetic diseases second-generation sequencing '. The analysis and interpretation of test data refer to the ' ACMG genetic variation classification criteria and guidelines ' issued by the American Society of Medical Genetics and Genomics (ACMG) in conjunction with the Molecular Pathology Society (AMP) and the domestic ' genetic variation classification criteria and guidelines (2017) '. The variation was divided into five grades : pathogenic (P, pathogenic possibility > 0.99), suspected pathogenic (LP, pathogenic possibility 0.95-0.99), unknown clinical significance (VUS, pathogenic possibility 0.01-0.90), suspected benign (LB, pathogenic possibility

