0.001-0.01), benign (B, pathogenic possibility < 0.001). The results of gene detection in this study only classified pathogenic and possible pathogenic mutations as positive mutations, and homozygotes and compound heterozygotes of autosomal recessive inheritance, single heterozygotes and homozygotes of autosomal dominant inheritance, and hemizygotes of X-linked inheritance were classified as disease positive. The unclear clinical significance is not directly used as the basis for clinical diagnosis. It is necessary to combine the clinical, if necessary, to carry out the corresponding family member verification, auxiliary examination, clinical follow-up.

(3) MS / MS data collection and standardization : The collected data include (1) laboratory background information including instrument type, reagent type, quality control material type, laboratory quality control rules, filter paper type, normal population range ; (2) Quality control data included quality control number, quality control type, quality control batch number, amino acid internal standard batch number, acylcarnitine internal standard batch number, factory time, experimental time, and test value of each quality control analyte ; (3) Screening test data include screening number, gestational age, breastfeeding method, native place (province, city), newborn gender, birth date, birth weight, sample number, blood collection time, etc. ; (4) The data of confirmed cases included screening number, confirmed disease, blood ammonia test, blood gas analysis, blood routine, liver function test, urine GC-MS test, imaging examination, gene detection information and other tests. The fluctuation range of the detection concentration of the corresponding batch of quality control samples was within the target value ± 3 s. Finally, the data were collected and sorted into the negative database and the positive database. In order to eliminate the influence of regional differences, the series detection index data were standardized.

(4) By analyzing the correlation between large sample gene data and tandem mass spectrometry data and the correction of clinical prognosis, a neonatal genetic disease gene screening database and an artificial intelligence risk assessment

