3.7 Statistical processing

IBM-SPSS 26.0 statistical software and R language (Version 4.1.0) were used for statistical analysis of the test results, and the positive rate of neonatal genetic disease screening (common positive disease cases, common positive sites) was counted. The carrying rate of common mutation sites in newborns was counted. The measurement data were expressed as mean \pm standard deviation ($x \pm s$), and t test was used for comparison between groups. The count variables were expressed as values or rates (%), and the comparison between groups was tested. Unconditional logistic regression analysis was used to evaluate the correlation between genotype and

clinical phenotype. Generalized multifactor dimensionality reduction (GMDR) was used to analyze gene-gene interaction and genotype-phenotype correlation. Based on tandem mass spectrometry data, machine learning algorithms such as random forest, support vector machine, elastic network, and multi-layer perceptron were used to construct genotype prediction models. Accuracy, Balanced accuracy, sensitivity, and specificity were used to evaluate the prediction effect of the model.

4. Ethics in clinical research

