4.1 Data source

The gene sequencing data and MS / MS metabolic data of 40,000 newborns were from 123 cooperative units of the South China Neonatal Gene Screening Alliance. In this study, the data table established by Microsoft Excel was used. The neonatal gene data and tandem mass spectrometry of the multi-center cooperative units were transmitted through the Excel data table. Effective measures will be taken to strictly record, clean and check the data. Multi-centers ensure the authenticity, accuracy and completeness of the neonatal gene sequencing data and MS / MS metabolic data provided, and all data and test reports can be traced. In addition, the data management, pay attention to the confidentiality of the data, to ensure the privacy of patients and their families.

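### The group comparisons in section 3.7 ignore which of the 123 units a newborn came from, leaving the genotype-metabolite and genotype-phenotype results open to confounding by site

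*Combined protocol and SAP*

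**What the plan says.** - **Data source.** The study "plans to include 123 cooperative units" (section 3.1 Research Design). The Sample size section gives "about 40,000 newborns from January 2019 to August 2022 in 123 cooperative units", with no derivation, and section 4.1 repeats that the data "were from 123 cooperative units of the South China Neonatal Gene Screening Alliance".
- **Tests.** For continuous data, section 3.7 says "t test was used for comparison between groups". For counts: "The count variables were expressed as values or rates (%), and the comparison between groups was tested", with no test named. For phenotype: "Unconditional logistic regression analysis was used to evaluate the correlation between genotype and" clinical phenotype. No covariate, centre term, stratum, random effect or cluster-robust variance appears. Positive and carrying rates are to be counted; no standard error or interval is mentioned anywhere.
- **Site differences.** Section 3.3 item (3) says of the MS/MS data: "In order to eliminate the influence of regional differences, the series detection index data were standardized". It gives neither the method nor the unit (hospital, laboratory or region). The same item collects instrument, reagent and quality-control details. Section 1.1 says the diseases and genes on a screening panel can be designed "according to regional or ethnic differences".
- **Use of the comparisons.** Section 3.6 item (5) contrasts the metabolic profiles of positive, carrier and negative newborns at high-frequency VUS sites and uses the result as evidence on pathogenicity.

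**The concern.** A plain t test and a logistic model without site terms treat every newborn as an independent draw from one population. Here newborns are grouped by unit, and both sides of the comparison may vary with the unit: metabolite values through laboratory and population, genotype through ancestry and region.

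Two things can follow. If both vary between units without being aligned, the t test's standard error is somewhat too small. If they are aligned, so that an area with more carriers also has higher or lower values of a metabolite, the test picks up a difference that genotype did not cause. The second is the more serious, because a metabolite shift at a VUS site is to be read as a sign of pathogenicity. The genotype-phenotype models carry the same risk, and the MS/MS standardisation does not reach them.

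**Working it through.** The plan states no alpha, power, precision target or ICC, so it has no figure of its own to reproduce. ICCs, clustering and regional shifts below are assumptions.

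**Inputs from the documents.** N = 40,000 and 123 units (Sample size section, section 4.1); high-frequency threshold 1% (section 3.6 item (3)); an illustrative positive rate of 4.0%, from the multi-centre project described in section 1.1. Mean cluster size m = 40,000/123 = 325.2.

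**1. Clustering in the t test.** For a comparison within hospitals, the variance inflation is approximately 1 + (m − 1) × ICC(metabolite) × ICC(variant).
- ICCs 0.01 and 0.02: 1 + 324.2 × 0.0002 = 1.065. The critical value is effectively 1.96/√1.065 = 1.90, so type I error is about 5.8%.
- ICCs 0.05 and 0.02: 1 + 324.2 × 0.001 = 1.324. Then 1.96/√1.324 = 1.70, so type I error is about 8.9%.

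Simulation of 123 × 325 newborns with 1% carriers agrees: 5-9% over metabolite ICC 0.01-0.05 and variant clustering 0-0.02 (400 runs per setting, Monte Carlo error about ±2 points). A repeat with 1,000 runs gave 5-8%. A hospital-adjusted test stayed at about 3-6% and about 5% respectively.

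**2. Confounding by region.** Assume two regions of 20,000, carrier rates 1% and 2%, no genotype effect, and a metabolite shift of d SD left after standardisation.
- Carriers: 200 + 400 = 600, of whom 400/600 = 0.667 are in region 2.
- Non-carriers: 19,800 + 19,600 = 39,400, of whom 0.497 are in region 2.
- Spurious difference = d × (0.667 − 0.497) = 0.169d.
- SE = √(1 + d²/4) × √(1/600 + 1/39,400) = √(1 + d²/4) × 0.0411.

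| d | Spurious difference (SD) | z | Rejection at 5% |
|---|---|---|---|
| 0 | 0 | 0 | 5% |
| 0.2 | 0.034 | 0.82 | 13% |
| 0.5 | 0.085 | 2.00 | 51% |

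**3. Rates, if a simple binomial interval were attached.** Design effect = 1 + (m − 1) × ICC, equal hospital sizes; coverage = 2Φ(1.96/√DE) − 1; between-hospital SD = √(ICC × p(1 − p)). Naive 95% half-widths are 0.19 percentage points (pp) at 4.0% and 0.10 pp at 1%.

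| ICC | DE | SE factor | Coverage | Half-width at 4.0% | Half-width at 1% |
|---|---|---|---|---|---|
| 0.001 | 1.32 | 1.15 | 91% | 0.22 pp | 0.11 pp |
| 0.005 | 2.62 | 1.62 | 77% | 0.31 pp | 0.16 pp |
| 0.01 | 4.24 | 2.06 | 66% | 0.40 pp | 0.20 pp |

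For a 1% site, ICC 0.01 means a between-hospital SD of √(0.01 × 0.01 × 0.99) = 0.995 pp, about as large as the rate itself, so that row is a high-end case. ICC 0.001 means an SD of 0.31 pp. Unequal hospital sizes increase the inflation: with a coefficient of variation of 1, DE at ICC 0.01 is 7.49.

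**The case against.** - **The rate intervals do not exist.** A reader might infer that the plan's intervals for positive and carrying rates are too narrow. The documents do not support that: section 3.7 counts rates and plans no interval. The third calculation describes an interval someone might add later. It also applies only if the 123 units stand for a wider population. If the target is these units alone, hospitals are fixed strata and this inflation does not arise. If the target is newborns in China, as section 3.1 suggests, a robust standard error still does not make a South China alliance representative. All of this stands.
- **The planned tests are mildly affected by clustering alone.** Carriers and non-carriers occur within the same hospitals, and 5-9% is modest. This stands; larger figures need carrier rate and metabolite level to shift together.
- **Standardisation is aimed at this problem.** If done within hospital or laboratory it could remove much of the metabolite confounding. This stands in part: the method and unit are unstated, and the step cannot touch genotype rates or the logistic models.
- **The text is silent rather than contrary.** Unconditional logistic regression does not exclude hospital covariates. The remark in section 1.1 concerns panel design and reports no differences among these hospitals; instrument and reagent are listed as collected items, not as shown sources of variation. This is fair, but a plan that collects such information should say how it is used.

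**Conclusion.** The point holds as a gap in the analysis of group comparisons. Section 3.7 has no term for hospital, laboratory or region, so genotype-metabolite and genotype-phenotype results are open to site confounding. Under the assumptions shown, the t test's error rate ranges from essentially nominal to about 9% from clustering alone, and to about 13-51% if carrier rate and residual metabolite level shift by region. If standardisation removes the whole shift, the regional component disappears. The documents give no ICC, hospital-size distribution or residual shift, so none of these is an estimate for this study; clustering may also act at laboratory or region level rather than hospital.

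On the rates, the supported statement is limited: no interval is planned, and a simple binomial one would be too narrow if rates vary between hospitals and inference goes beyond these units. This deserves correction before analysis, but it does not invalidate the descriptive counts.

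**What to change.** In section 3.7:

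1. Replace the plain t test with a linear model that includes hospital or testing laboratory as a fixed effect or stratum, with cluster-robust standard errors. A random intercept alone may not remove confounding.
2. Add the same term to the logistic models: condition on hospital, or use region or laboratory where hospital strata are too sparse. A 1% variant gives only about 3 carriers per hospital (325 × 0.01).
3. Report the overall positive rate, the carrying rate and the high-frequency-site rates with 95% intervals that allow for between-hospital variation. Use exact binomial intervals for diseases with very few or no cases, where a cluster-robust interval breaks down.
4. State the method and unit of the MS/MS standardisation in section 3.3.
5. Keep the contributing unit as a field in the pooled table. The listed variables do not include it, although section 4.1 has units sending their own traceable data, so it should be recoverable.

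The cost is a little more analysis work, in R, which the plan already names, and somewhat wider intervals. No ICC is needed in advance, and if site differences are negligible the results will barely change.

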research object	Gene screening data of 40,000 newborns (138 genes related to 133 common genetic diseases) and tandem mass spectrometry data (11 amino acids and 28 acylcarnitines).
Inclusion criteria	(1) Newborns who underwent genetic screening and tandem mass spectrometry at the same time. (2) Age : 0-28 days, gestational age 37-42 weeks.
Excluded criteria	Data that meets any of the following conditions need to be eliminated : (1) Neonatal data with unclear clinical basic information ; (2) Lack of traceability core information data ; (3) The data that the test results cannot be analyzed and interpreted.
sample size	Gene screening and tandem mass spectrometry data of 40,000 newborns.
data collection	(1) Basic information : gender, age, sample type, subject traceability number / ID number, etc. (2) Clinical symptoms, biochemical and imaging data of positive samples. (3) Gene detection results and tandem mass spectrometry results.

	(4) Date of test data, instrument model, reagent type, etc.
Statistical processing	IBM-SPSS 26.0 statistical software was used to analyze the test results. Logistic regression analysis was used to evaluate the correlation between genotype and clinical phenotype. Generalized multifactor dimensionality reduction method was used to analyze gene-gene interaction and genotype-phenotype correlation. Based on tandem mass spectrometry data, machine learning algorithms such as random forest, support vector machine, elastic network, and multi-layer perceptron were used to construct a genotype prediction model. The prediction effect of the model was evaluated by accuracy, balance accuracy, sensitivity, and specificity.
abbreviation	Principal Investigator, PI; tandem mass spectrometry, MS/MS; Inborn errors of metabolism, IEM

1. project basis

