lower, which makes it possible for gene detection technology to screen newborns. In the past ten years, genetic screening technology has been widely used in many countries such as Europe and the United States, such as preimplantation genetic screening, prenatal screening, neonatal screening, hypertension gene screening, familial hypercholesterolemia gene screening, etc. The results of screening are satisfactory. In 2016, the Chinese Neonatal Genome Project was initiated by the Genetic Counseling Branch of the Chinese Genetic Society and the Children 's Hospital of Fudan University in Shanghai. The program will carry out 100,000 samples of neonatal genetic testing within 5 years, aiming to build a Chinese neonatal genome database, establish neonatal genetic testing standards, promote the industrialization of neonatal genetic testing, and improve the genetic counseling training system. Since the launch of the program, the results have been remarkable. In 2018, [name] 's team of Children 's Hospital Affiliated to Fudan University, head of the Neonatology Group of the Pediatrics Branch of the Chinese Medical Association, took the lead in carrying out a clinical-related whole exome sequencing gene screening research project for newborns. The project has achieved significant results. The data show that genetic testing technology can greatly improve the positive rate of genetic disease screening. In 2020, [name], former director of the Pediatrics Branch of the Chinese Medical Association, also conducted neonatal genetic screening research. More than 2500 known pathogenic mutation sites of 135 genes in 75 common genetic diseases were used as detection targets. The data of samples from North China, Northwest, Southwest, Central South and East China showed that the positive detection rate of pathogenic mutations was 2.3 %, and the carrying rate was 26.6 %. [name] and his team explored a large-scale and large-scale gene screening model based on hot spot mutation detection. In the same year, the ' Beijing neonatal disease screening management method ' clearly included deafness gene screening into the screening content of the neonatal disease screening management method. In early 2021, led by [name] of Xinhua Hospital Affiliated to Shanghai Jiao Tong University and the head of the new screening center of Shanghai Institute of

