3.6 Observation items

(1) Positive detection rate of common genetic diseases in neonates : the results of genetic testing of enrolled neonates showed that the proportion of homozygous and compound heterozygotes of autosomal recessive inheritance, single heterozygote and homozygous of autosomal dominant inheritance, and hemizygote of X-linked inheritance accounted for the total number of people tested.

(2) The corresponding pathogenic genes and pathogenic variation carrying rate of common neonatal genetic diseases : that is, the proportion of the total number of occurrences of pathogenic variation, suspected pathogenic variation and

unknown clinical significance variation in the genetic test results of the enrolled neonates according to the ' ACMG genetic variation classification criteria and guidelines ' and ' genetic variation classification criteria and guidelines (2017) '.

- (3) The carrying rate of high-frequency mutation sites in the population : that is, the mutation sites with a population carrying rate greater than 1 %.
- (4) Establish a complete protein structure and catalytic activity analysis process, and develop artificial intelligence protein analysis tools for pathogenicity prediction of mutation sites.
- (5) Preliminary identification of the pathogenicity of high-frequency VUS mutation sites : The protein structure and enzyme catalytic activity characteristics of high-frequency VUS mutation sites were predicted by artificial intelligence tools, and the metabolic spectrum differences between positive, carrier and negative samples of high-frequency VUS mutation sites were clarified by combining with tandem mass spectrometry metabolite data, which provided a basis for the pathogenicity judgment of VUS mutation.
- (6) Gene-metabolism correlation : machine learning algorithms such as random forest, support vector machine, elastic network and multi-layer perceptron are used to construct prediction models of common genetic diseases, so as to realize accurate diagnosis of common genetic diseases through tandem mass spectrometry metabolomics data, and expand 2-3 diseases that can be diagnosed by tandem mass spectrometry.

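### Section 3.7 leaves gene-gene interaction to GMDR alone, but a significant two-gene GMDR model can come from one gene's effect and is not evidence of interaction

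*Combined protocol and SAP*

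**What the plan says.** Section 3.7 gives the method one sentence, repeated almost unchanged in the abstract: "Generalized multifactor dimensionality reduction (GMDR) was used to analyze gene-gene interaction and genotype-phenotype correlation". The sentence before it plans unconditional logistic regression of clinical phenotype on genotype. No other method is tied to gene-gene interaction.

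The plan does not state, for GMDR, the phenotype, the genes or sites entered, the model order, covariates, cross-validation, the significance test and its null, a minimum cell count, or any adjustment for the number of pairs.

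Other relevant text:
- Sample size section: "This study plans to collect genetic screening data (138 genes related to 133 common genetic diseases"). The abstract gives the size as "Gene screening and tandem mass spectrometry data of 40,000 newborns".
- Section 3.6 (3) defines high-frequency sites as "the mutation sites with a population carrying rate greater than 1" per cent, with no upper value.
- Section 3.3 (2) calls genotypes gene by gene according to mode of inheritance; those meeting the rule "were classified as disease positive".

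**The concern.** GMDR pools the genotype combinations of several genes into high-risk and low-risk groups and asks whether the pooled classifier predicts the phenotype. Under the usual permutation test, the phenotype is shuffled freely, so the null is that none of the genes matters. If one gene has an effect, every two-gene model containing it can reject that null, whatever the second gene does. Rejection therefore does not separate an interaction from a single-gene effect. Strong single-gene effects are plausible on a panel built around single-gene diseases.

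Information on interaction comes mainly from newborns who carry variants at both sites of a pair. With low carriage at each site that cell is small even in 40,000 newborns.

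At stake is a published list of gene-gene interactions that may be only the effect of one causal gene paired with other genes.

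**Working it through.** The plan has no power or sample-size figure for GMDR, so there is nothing of its own to reproduce.

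**1. Double carriers per pair**

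Inputs: N = 40,000; 138 genes, hence 138 × 137 / 2 = 9,453 possible pairs. Section 1.1 cites these overall carrying rates, in per cent:
- the team's preliminary study: "A total of 972 cases carried one or more gene pathogenic variation sites, with a carrying rate of 54.21";
- a 159-gene multicentre study: "the positive detection rate is close to 4.0 %, and the carrying rate is 51.98";
- a 135-gene hot-spot study: "the positive detection rate of pathogenic mutations was 2.3 %, and the carrying rate was 26.6".

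Assume equal, independent genes and apply each rate to this panel. The per-gene rate q solves 1 − (1 − q)^138 = overall rate, and expected double carriers per pair are 40,000 × q².

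| Overall rate | q | Double carriers per pair |
|---|---|---|
| 54.21% | 0.564% | 1.27 |
| 51.98% | 0.530% | 1.12 |
| 26.6% | 0.224% | 0.20 |

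At 54.21%, the chance that a pair has no double carrier is exp(−1.27) = 28%. Unequal gene frequencies do not raise the average over pairs above about 1.3. (972 / 1,739 is 55.89%, not 54.21%; 55.89% gives q = 0.591% and 1.4 double carriers, so nothing changes.)

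**2. What a pair can show**

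The phenotype is unstated, so take a binary one with prevalence p = 8.81%, the preliminary study's positive rate, as a favourable assumption. The variance of the interaction log odds ratio is the sum, over the four carrier cells of size n, of 1/(np) + 1/(n(1 − p)). The odds ratio detectable with 80% power at two-sided 0.05 is exp[(1.96 + 0.84) × SE].

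| Carriage at both sites | Double carriers | Affected double carriers | Detectable odds ratio | Same, Bonferroni for 9,453 pairs |
|---|---|---|---|---|
| 1% | 4 | 0.35 | 147 | about 14,900 |
| 2% (assumed) | 16 | 1.4 | 12.4 | 128 |
| 5% (assumed) | 100 | 8.8 | 2.8 | 7.4 |
| 10% (assumed) | 400 | 35 | 1.7 | 2.9 |

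At an assumed 1% prevalence, two 5% sites have 1 affected double carrier and a detectable odds ratio of about 19. For two 1% sites the interaction is then effectively not estimable.

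**3. Single-gene effect only, no interaction: how often is the two-gene model significant?**

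All runs use 40,000 newborns, carrier/non-carrier coding and two independent sites, only one of which has an effect.

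*Continuous phenotype, 1% sites* (10-fold score classifier, 19 free permutations, 120 runs per effect):

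| Effect of the one site | Two-gene model significant |
|---|---|
| none | 2.5% |
| 0.1 SD | 25% |
| 0.2 SD | 69% |
| 0.3 SD | 96% |
| 0.5 SD | 100% |

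A regression product term rejected in 4.4% of 2,705 runs with at least 2 double carriers. A separate repeat gave 64% and 100% at 1% carriage (0.2 and 0.5 SD) and 100% for both effects at 5% carriage. It gave 3-10% when permutation kept the single-gene effect.

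*Binary phenotype* (10-fold balanced accuracy, 39 permutations, 60 runs):

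| Carriage | Baseline prevalence | Odds ratio, one gene | Free permutation | Permutation within strata of that gene |
|---|---|---|---|---|
| 0.56% | 1% | 5 | 87% | 7% |
| 0.56% | 0.1% | 50 | 100% | 10% |
| 1% | 1% | 5 | 100% | 7% |
| 1% | 8.81% | 3 | 100% | 5% |
| 5% | 1% | 5 | 100% | 0% |
| 5% | 1% | 2 | 85% | 3% |
| 1% | 1% | 1 (none) | 2% | 0% |
| 5% | 1% | 1 (none) | 5% | 10% |

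With 60 runs the Monte Carlo half-width around 5% is about 6 points, so the last column is compatible with 5%. Changing only the null removes the excess, and the excess is also present at 5% carriage. The cause is the null of no association, not sparse cells alone.

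**The case against.** The strongest reply is that much of this is supplied by the reader. Section 3.7 states no null, so a permutation that keeps single-gene effects is not excluded. No scan of all 9,453 pairs is planned either. This stands: a reader might infer that the plan as written will report false interactions, but that follows only under GMDR's usual null, which the plan neither adopts nor rules out.

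A reader might also infer that GMDR is aimed at rare variants and that double carriers are almost absent. The documents do not restrict the sites entered. The 1.3 is an average pair and the 4 is the floor of the high-frequency definition. By the same binomial assumption about 18% of newborns (about 7,300) carry variants in two or more genes. Carriers are scarce per pair, not overall.

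The disease-positive rule in section 3.3 (2) is a rule for calling genotypes. Nothing makes it the GMDR phenotype.

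GMDR is also planned for genotype-phenotype correlation, and a signal driven by one gene is a legitimate result there.

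Finally, GMDR in practice often chooses between one-gene and two-gene models, which the runs above did not do. With that step added (two 1% sites, 150 runs), the two-site model still beat the one-site model in 37%, 35% and 23% of no-interaction runs at 0.2, 0.3 and 0.5 SD. With a search over 8 sites it did so in 43-52% (60 runs). The rate depends on the decision rule, but comparison with the best one-gene model is not a sufficient safeguard.

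**Conclusion.** The point holds in this form: the plan relies on GMDR alone for gene-gene interaction, and under that method's usual test a significant two-gene model does not show interaction. The false-finding rate was about 64-100% for single-site effects of 0.2-0.5 SD at 1% carriage, and the problem persists at 5%. Separately, most pairs on the panel hold too few double carriers to be assessed.

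This rests on the no-association null, independent sites, carrier coding, the cited carrying rates applying to this panel, and the effect sizes and prevalences shown. The simulations are modest in size, but rates of 64% or more are far outside Monte Carlo error around 5%.

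The documents do not support the stronger reading that GMDR is the wrong method altogether, or that no pair can be studied. The consequence is limited: gene-gene interaction appears only as a method in the abstract and section 3.7, and in no objective or observation item.

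**What to change.** Amend section 3.7, and the matching abstract row, to:
- name the phenotype and the sites eligible for interaction analysis;
- claim gene-gene interaction only from a test conditional on both single-gene effects. This can be a product term added to both single-gene terms in the regression for the plan's own phenotype (penalised or exact if cells are sparse), or a permutation that preserves both main effects. Permuting within strata of one gene, as in the check above, keeps only that gene's effect;
- restrict testing to site pairs with a prespecified minimum number of double carriers, justified by precision. As a guide, 20 double carriers need about 2.2% carriage at both sites (40,000 × 0.0224² = 20). For a continuous phenotype that gives an interaction SE of about √(1/20 + 2/875) = 0.23 SD, so about 2.8 × 0.23 = 0.64 SD is detectable with 80% power before any adjustment. The team should decide whether that is good enough;
- adjust for the number of pairs actually tested;
- keep GMDR as descriptive, for genotype-phenotype correlation.

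The cost is SAP wording, one extra model per eligible pair, and fewer pairs tested. No new data are needed.
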